### **Adverse events requiring specific monitoring**

An AE requiring specific monitoring is a serious or non-serious AE of scientific and medical concern specific to the Sponsor's product or program, for which ongoing monitoring may be appropriate. Such events may require further investigation to characterize and understand them. These events should be reported on the AE page and additional information required on specific e-CRF page (where applicable) and will only qualify for expedited reporting when serious (fulfilling SAE criteria).

The AEs requiring specific monitoring for this study are:

- Severe GI events
- Severe hypoglycemia (see [Section 8.2.5](#))
- Pancreatic events (including abnormal values of pancreatic enzymes [see Appendix 5, [Section 10.5.2](#)] pancreatitis, and pancreatic neoplasm ) – will be adjudicated by CEC
- Major adverse cardiovascular events (MACE; cardiovascular (CV) death, myocardial infarction (MI), or stroke) and other specific CV events (eg, heart failure leading to hospitalization) – will be adjudicated by CEC
- Calcitonin increase  $>5.9$  pmol/L (20 pg/mL) and thyroid C-cell neoplasm (see Appendix 5, [[Section 10.5.3](#)])
- Acute renal failure (see Appendix 5 [[Section 10.5.4](#)] for definition)
- Diabetic retinopathy complications (will be reviewed by an independent ophthalmologist expert; see Appendix 1 [[Section 10.1.4.3](#)])); a written report from professional eye care provider will be required
- Severe injection site reaction
- Severe allergic reactions
- Severe immune complex disease

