## **10.5.2 Monitoring of participants with increased lipase and/or amylase >2 ULN**

GLP-1 RAs stimulate pancreatic beta-cell and suppress alpha-cell function. Some cases of acute pancreatitis have been reported with marketed GLP-1 RAs. Therefore participants enrolled in this study should be closely monitored for any suspected pancreatitis, eg, with symptoms and/or signs of acute abdominal distress or abnormal levels of pancreatic enzymes. Serum amylase and lipase concentrations are monitored routinely at Screening, Baseline and periodically during the study treatment period.

In the presence of clinical signs and/or symptoms evocative of pancreatitis, eg, persistent abdominal pain, which can radiate to the back, often with characteristic positional features, with possible occurrence of nausea, vomiting, fever, and leucocytosis, further measurement of amylase and lipase should be performed. The clinical signs and/or symptoms should be documented in the source data.

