#### **10.5.2.2 Elevation of amylase and/or lipase $>2 \times$ ULN with clinical signs and/or symptoms.**

In the presence of clinical signs and/or symptoms evocative of pancreatitis (as previously described) associated with elevated amylase and/or lipase, treatment with the IMP should be promptly and at least temporarily discontinued pending further clinical evaluation and diagnosis confirmation. Clinical signs and/or symptoms are to be documented in the source data.

A laboratory determination of amylase and lipase must be obtained at the time of the event and again within 48 hours or earlier as clinically indicated. If the value(s) remain(s)  $>2 \times$  ULN, then amylase and/or lipase levels should be retested as described in Appendix 5 [Section 10.5.2.1](#) or more often if clinically indicated.

A gastroenterologic evaluation and imaging (ultrasound and/or CT or MRI with contrast, as appropriate) must be performed as clinically indicated and as per clinical practice and local guidelines. If a diagnosis of pancreatitis is confirmed, IMP should not be restarted and should be permanently discontinued.

In both cases ([Section 10.5.2.1](#) and [Section 10.5.2.2](#)) as previously described, all laboratory or clinical documentations are to be collected. If the retest confirms lipase and/or amylase values are  $>2$  ULN, the event must be reported in the e-CRF on the specific AE form and the specific complementary forms, using the appropriate verbatim: eg, “increased amylase and/or lipase” in case of isolated enzyme elevation, “suspected pancreatitis” in the presence of clinical signs evocative of pancreatitis if the diagnosis is suspected but cannot be confirmed or excluded, and “pancreatitis” if the diagnosis has been confirmed.

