Adverse events of special interest (AESIs) include the following:

- Pregnancy of a female participant entered in a study as well as pregnancy occurring in a female partner of a male participant entered in a study with IMP/NIMP;
- Symptomatic overdose (serious or nonserious) with IMP/NIMP;
- Increase in alanine aminotransferase (ALT) $>3 \times$ upper limit normal (ULN).

Adverse events requiring specific monitoring include the following terms:

- Severe gastrointestinal (GI) events;
- Severe hypoglycemia;

- Pancreatic events (including abnormal values of pancreatic enzymes, pancreatitis and pancreatic neoplasm);
- Selected cardiovascular events (CV death, MI, stroke, heart failure leading to hospitalization, unstable angina, and transient ischemic attack [TIA]);
- Calcitonin increase (≥ 5.9 pmol/L (20 pg/mL)) and thyroid C-cell neoplasm;
- Acute renal failure;
- Diabetic retinopathy complications;
- Severe injection site reaction;
- Severe allergic reactions;
- Severe immune complex disease.

Independent Clinical Endpoint Committee(s) [CEC(s)] will review, assess and/or adjudicate all events of death, selected CV events and pancreatic events.

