Severe hypoglycemia	Any hypoglycemia event which required assistance (from hypoglycemia page)
Pancreatic event	Cases reported in eCRF “Suspected or confirmed Pancreatitis” page or AE Category = “Pancreatic Neoplasm”

AE Grouping	Criteria
Selected cardiovascular event	Cases reported in the following specific eCRF pages: 
• "Suspected or confirmed MI/Unstable Angina"• "Suspected or confirmed cerebrovascular event"• "Suspected or confirmed heart failure" led to unplanned hospitalization, led to urgent/unscheduled visit to emergency room or an urgent/unscheduled outpatient heart failure treatment unit, or infusion center, or office/practice visit, not followed by hospitalization, or occurred while patient was hospitalized for another reason• Primary cause of death in eCRF "Death (CV)" as Acute MI, Sudden cardiac death, Heart failure or cardiogenic shock, Stroke, Complication of cardiovascular procedure, Other cardiovascular cause, or Undetermined cause of death
Calcitonin and thyroid C-cell neoplasm	Using Calcitonin increase CMQ
Acute renal failure	Using Acute renal failure CMQ
Severe injection site reaction	Intensity = "Severe" + Using Injection site reaction_ CMQ.
Severe allergic reaction	Intensity = "Severe" + CMQs for anaphylactic reaction, angioedema, severe cutaneous adverse reaction, anaphylactic/anaphylactoid shock conditions (under SMQ "Shock"), and hypersensitivity.
Severe immune complex disease	Intensity = "Severe" using Immune complex disease CMQ
Diabetic retinopathy complications	Cases reported in eCRF "Diabetic Retinopathy Complementary Form"

The following TEAE summaries will be generated for the safety population:

- All AESI by prespecified grouping and PT, showing number (%) of participants with at least 1 AESI, with PTs sorted by decreasing order in Efpeglenatide 6 mg group.
- All AERSM by prespecified grouping and PT, showing number (%) of participants with at least 1 AERSM, with PTs sorted by decreasing order in Efpeglenatide 6 mg group.

Separate AESI listings will be provided for pregnancy, overdose, and ALT increase, as well as an overall listing for AERSM.

Analysis of adjudicated events

All events of death, selected cardiovascular events (MI, stroke, unstable angina leading to hospitalization, and heart failure leading to hospitalization), any pancreas-related events, and other selected AEs (as defined in the CEC charter) will be reviewed, assessed and adjudicated by CEC.

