2.4.5.5 Analyses of laboratory variables

All hematology and clinical chemistry results will be listed by treatment group, participants and visit, including scheduled and unscheduled/repeat measurements.

The summary statistics (including number, mean, median, standard deviation, minimum and maximum) of all protocol-required laboratory variables (central laboratory values and changes from Baseline) will be calculated for each scheduled visit and last value on treatment by treatment group.

The incidence of PCSAs at any time during the whole on-treatment period will be summarized by biological function and treatment group whatever the Baseline level and/or according to the following Baseline status categories:

- Normal/missing
- Abnormal according to PCSA criterion or criteria

For parameters for which no PCSA criteria are defined, similar table(s) using the normal range will be provided. For calcitonin, no PCSA criterion is defined. Similar summaries will be provided using the pre-defined categories: \leq ULN, $>$ ULN - $<$ 20 ng/L, \geq 20 - $<$ 50 ng/L, and \geq 50 ng/L (Note that ng/L is the standard international unit and is equivalent to pg/mL).

All measurements collected during the whole on-treatment period, including values from unscheduled visits, will be considered for the PCSA summaries. These summaries will include participants in the safety population who have at least 1 assessment performed during the whole on-treatment period. When a PCSA definition involves only a change from baseline value, participants must also have a baseline value to be included in the summaries, and when required by the definition of the abnormality, participants must also have available laboratory normal ranges.

For some parameters, such as liver enzymes, the lower limit of normal (LLN) is not considered clinically relevant, and values below this limit are considered normal. When there are multiple PCSA criteria for a specific parameter (eg, ALT), the participant will be counted once during the whole on-treatment period for the specific parameter in question under the worst/maximum PCSA category.

Elevated liver parameters will be summarized by treatment group in safety population.

For PCSA, both central and local lab data will be used.

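### SAP Table 3 states no route for isolated pancreatic enzyme rises into the pancreatic AERSM count, although SAP 2.1.4 and the protocol both include them

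*SAP*

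**What the plan says.** **Protocol definition.** Section 8.3 lists, among the events requiring specific monitoring, "Pancreatic events (including abnormal values of pancreatic enzymes", together with pancreatitis and pancreatic neoplasm. It refers to Appendix 5, Section 10.5.2, whose title gives the threshold: "Monitoring of participants with increased lipase and/or amylase >2 ULN".

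**Protocol reporting rule.** The close of 10.5.2.2 covers both the asymptomatic and the symptomatic case. Once a retest confirms a value above 2 ULN, "the event must be reported in the e-CRF on the specific AE form and the specific complementary forms, using the appropriate verbatim". Three wordings are offered. The first is "increased amylase and/or lipase” in case of isolated enzyme elevation"; the other two are for suspected pancreatitis, where clinical signs are present, and for confirmed pancreatitis.

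**SAP definition.** Section 2.1.4 carries the protocol's scope forward: "Pancreatic events (including abnormal values of pancreatic enzymes, pancreatitis and pancreatic neoplasm".

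**SAP criteria.** Section 2.4.5.1 says that the AERSM are the events of 2.1.4 and that their criteria are in Table 3. The pancreatic row reads "Cases reported in eCRF “Suspected or confirmed Pancreatitis” page or AE Category = “Pancreatic Neoplasm".

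**SAP laboratory cut.** Appendix B sets the potentially clinically significant abnormality (PCSA) for both lipase and amylase at ≥3 ULN.

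**The concern.** The definition has three components: abnormal enzymes, pancreatitis and neoplasm. Table 3 gives an explicit criterion for two of them. Protocol 10.5.2 treats an isolated enzyme rise as an event in its own right, with its own reported term. The page named in Table 3 matches, by its title, only the suspected-pancreatitis and pancreatitis terms.

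Pancreatitis is a named class risk in protocol 2.3 and 10.5.2. A monitored category exists so that a reader can see its events together, by treatment group, without rebuilding them from general preferred-term rows. If the row is programmed as written, it may report fewer pancreatic events than the SAP's own definition calls for. Two programmers could also reasonably derive different counts from the same data.

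**Working it through.** No power, alpha or event figure in the documents bears on this point, so there is nothing to reproduce numerically. The check sets definitions and thresholds side by side and follows an isolated, retest-confirmed rise above 2 ULN through each planned output.

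| Planned output (SAP section) | Peak >2 to <3 ULN | Peak ≥3 ULN |
|---|---|---|
| AERSM table by grouping and preferred term (2.4.5.1) | No stated route | No stated route |
| AERSM line of the TEAE overview (2.4.5.1) | No stated route | No stated route |
| AERSM listing (2.4.5.1) | No stated route | No stated route |
| All-TEAE tables by preferred term (2.4.5.1) | Counted if treatment-emergent | Counted if treatment-emergent |
| Adjudicated events (2.4.5.1) | In scope; summary shows confirmed events only | Same |
| PCSA incidence (2.4.5.5, Appendix B) | Not counted | Counted |
| Laboratory listing and by-visit statistics (2.4.5.5) | Present as values, not as a count | Same |

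Four things follow.

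1. **The Table 3 gap does not depend on the size of the rise.** The first three rows are the same in both columns, because Table 3 names no enzyme criterion at any level.
2. **The 2 to 3 ULN band is a separate, smaller matter.** It concerns only the PCSA table, where no incidence row uses the protocol's 2 ULN threshold.
3. **Other laboratory-based items in Table 3 do have a stated route.** The ALT increase uses an eCRF checkbox and calcitonin uses a customized MedDRA query. The enzyme component of pancreatic events has neither.
4. **The PCSA baseline split has no clear place for a baseline of 2 to 3 ULN.** Exclusion criterion E10 (protocol 5.2) removes only screening values above 3 ULN, so such participants can be enrolled. The split in 2.4.5.5 offers normal or missing, and abnormal by PCSA; a value above 2 but below 3 ULN is neither normal nor abnormal by that criterion.

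**The case against.** **The page may already capture these events.** The protocol sends every confirmed rise, including asymptomatic ones, to complementary forms as well as the AE form, and the pancreatitis page is the only pancreas-specific eCRF page that either document names. If it is the complementary form, Table 3 already includes isolated rises, and the display by preferred term would separate them from pancreatitis. This is plausible. Neither document says it, however, and the page title points the other way.

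**The narrowing may be deliberate.** SAP Table 2 records that version 3 clarified the pancreatic event definition. That is possible, but the same entry labels dropped analyses as removed, and 2.1.4 still includes enzymes. If narrowing was meant, 2.1.4 needs to change.

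**Stronger readings.** A reader might infer that confirmed rises between 2 and 3 ULN are counted nowhere. The documents do not support that: the AE form is mandatory, so treatment-emergent rises appear in the all-TEAE tables. The SAP also places pancreas-related events within the adjudication scope and plans a listing of all adjudicated AEs with outcome.

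A reader might also infer that new and pre-existing elevations cannot be told apart. That goes too far. The TEAE definition requires onset or worsening on treatment, changes from baseline are summarized by visit, and every chemistry result is listed by participant.

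Nor is a ≥3 ULN PCSA cut an error merely because it differs from a reporting threshold. The calcitonin comparison is weak support for changing it. The SAP says "For calcitonin, no PCSA criterion is defined. Similar summaries will be provided using the pre-defined categories", and those categories do use the protocol's 20 and 50 pg/mL values, but lipase and amylase already have a PCSA criterion.

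**Conclusion.** The point holds as an inconsistency between SAP 2.1.4 (with protocol 8.3 and 10.5.2) and SAP Table 3. One of three defined components has no stated route into the pancreatic AERSM row, and three outputs inherit the gap.

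Its size depends on one undocumented fact, namely whether the pancreatitis page is also completed for isolated enzyme rises. If it always is, no events are lost and only the wording is unclear. If it never is, every isolated confirmed rise, whatever its level, is missing from the AERSM table, the overview line and the listing. The documents give no rate for such rises, so no participant count can be attached. The affected outputs are descriptive safety displays; no efficacy test is touched.

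The missing >2 ULN laboratory row is a secondary improvement, not a contradiction.

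**What to change.** **Main change, SAP Table 3.** Add to the pancreatic event row the AE of increased lipase and/or amylase with a retest-confirmed value above 2 ULN, shown on its own sub-row apart from suspected or confirmed pancreatitis and from neoplasm. If the pancreatitis page already captures isolated rises, say so in Table 3 and keep the separate display. If the narrowing was intended, amend 2.1.4 to match and state the departure from protocol 8.3.

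**Secondary change, SAP 2.4.5.5.** Add a descriptive >2 ULN row for lipase and for amylase, split by baseline ≤2 ULN versus >2 ULN.

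**Cost.** SAP wording and a few extra table rows, built from AE and laboratory data already collected. No clinical threshold or participant procedure changes.

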#### **10.5.3 Management of participants with increased calcitonin values**

During the course of the study if calcitonin value is found  $\geq 20$  pg/mL (5.9 pmol/L):

- A retest should be performed by the central laboratory within 7 days
- The following is to be collected and recorded as soon as possible:
  - Conditions other than C-cell disease which may increase calcitonin levels, such as: smoking status, treatment with proton-pump inhibitor (eg, omeprazole), autoimmune thyroid diseases (Hashimoto’s thyroiditis or Grave’s disease), differentiated thyroid cancer, hypercalcemia, hypergastrinemia, chronic renal insufficiency (not on dialysis), other neuro-endocrine tumors (lung small cell carcinoma, intestinal carcinoid), acute pulmonary inflammatory conditions, or sepsis
  - Personal and/or familial medical history in relation with thyroid or other endocrine diseases
  - Specific physical examination (neck, thyroid gland)

If the retest confirms that calcitonin value is  $\geq 20$  pg/mL:

- The event must be reported in the e-CRF on the AE form (as final diagnostic if available or as “increased calcitonin”); all appropriate clinical and laboratory documentations should also be reported in the corresponding eCRF pages

- An ultrasound scan of the thyroid is highly recommended to be performed and the participant may be referred to a Specialist if judged necessary (per clinical practice and local guidelines)
- The participant should continue to be followed according to protocol schedule (including planned calcitonin measurements). The AE form and all other related eCRF pages should be updated with any new information collected during the follow-up
- If calcitonin value  $\geq 50$  pg/mL (14.75 pmol/L) is found at any time during follow-up, **the participant should be permanently discontinued from IMP** and referred to a specialist. As far as possible, blood should be collected 1 to 2 weeks after IMP discontinuation and sent to the central laboratory for calcitonin measurement. As per protocol, the participant should be followed according to study procedures up to the scheduled end of the study

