- The frequency of TEAEs over time will be provided for nausea, vomiting, and diarrhea, using weekly time intervals through Week 8 and then every 4 weeks through Week 56, ie, [0-1] week, [1-2] weeks, [2-3] weeks, [3-4] weeks, etc. In each time interval, the numerator in the calculation of percentages will be the number of participants with at least 1 TEAE occurring in this time interval. Two types of analyses will be included: (1) only

the first event will be counted for each participant and all recurrent events will not be included, and the denominator for the calculation of percentages will be the number of participants at risk at the beginning of the time interval who did not experience a first event in the preceding intervals; and (2) the recurrent events in subsequent intervals will be counted once for each participant in the numerator of the corresponding interval, and the denominator for the calculation of percentages will be the number of participants at risk at the beginning of the time interval. A histogram of the frequency over time (by weekly intervals) will also be presented as appropriate.

- All TEAEs by BMI subgroup (< 30, \geq 30 kg/m²)
- All TEAEs by Anti-Efpeglenatide Antibody Status (Positive, Negative)

Analysis of all treatment emergent serious adverse event(s)

- All serious TEAEs by primary SOC, HLGT, HLT, and PT, showing the number (%) of participants with at least 1 serious TEAE

All serious TEAEs related to IMP, by primary SOC and PT, showing the number (%) of participants with at least 1 serious TEAE.

Analysis of all treatment-emergent adverse event(s) leading to treatment discontinuation

All TEAEs leading to treatment discontinuation, by primary SOC, HLGT, HLT, and PT, showing the number (%) of participants

Analysis of adverse events of special interest and adverse events requiring specific monitoring

Adverse events of special interest (AESI) and adverse events requiring specific monitoring (AERSM) include AE defined in [Section 2.1.4](#) and the criteria of AESI and AERSM are in [Table 3](#).

Table 3 - Criteria for AESI and AERSM

AE Grouping	Criteria
AESI	
Pregnancy	“Pregnancy” or “Partner pregnancy” checked
Symptomatic Overdose	“Overdose” checked and symptomatic (AEOVSYMP) = “Yes”
Increase in ALT >3 ULN	“ALT Increase” checked and Yes to the question “Is the event an AESI?” in eCRF form “Adverse Events”
AERSM	
Severe GI event	AE severity = “severe” using Gastrointestinal disorders CMQ

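### SAP Table 3 counts the calcitonin and thyroid C-cell neoplasm event only through a calcitonin-increase query, so cases reported under a diagnosis can be missing from that row

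*SAP*

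**What the plan says.** **Definition.** SAP section 2.1.4 lists among the AERSMs a calcitonin increase (at or above "20 pg/mL)) and thyroid C-cell neoplasm"). Protocol section 8.3 lists the same two-part event, ending "pmol/L (20 pg/mL) and thyroid C-cell neoplasm", but with a strict greater-than sign before the threshold.

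**Counting rule.** SAP section 2.4.5.1 states that "the criteria of AESI and AERSM are in" Table 3. The row labelled for calcitonin and thyroid C-cell neoplasm has one criterion: "Using Calcitonin increase CMQ". It names no neoplasm query, adverse event category, eCRF page or laboratory value. The SAP does not list the query's terms; its version history (section 1.6) says only that CMQs were brought into these definitions.

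**Reporting rule.** Protocol section 10.5.3 requires a retest after a value of 20 pg/mL or more. If the retest confirms it: "The event must be reported in the e-CRF on the AE form (as final diagnostic if available"; otherwise the term is increased calcitonin. The same section has sites record "Conditions other than C-cell disease which may increase calcitonin levels", and names autoimmune thyroid disease, differentiated thyroid cancer, chronic renal insufficiency and others.

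**The concern.** A two-part definition is put into operation by a query named for one part, and the reporting rule steers diagnosed cases away from the term that the query is named for. A site that follows the protocol exactly may enter no calcitonin term for a participant who meets the SAP's own threshold.

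What is at stake is how one safety row is read. Protocol section 2.3 cites a class box warning in the US label for thyroid C-cell tumours and commits to monitoring calcitonin throughout the study. A zero in a row carrying this label will be taken to mean that no participant had a confirmed rise or a C-cell neoplasm. The row also feeds the AERSM line of the TEAE overview, the AERSM table by grouping and preferred term, and the AERSM listing.

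**Working it through.** No power or alpha figure bears on this point, so the check is a reconciliation of text. It assumes that a CMQ selects events by their adverse event term.

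**Step 1. Which text governs the count?** Section 2.4.5.1 refers back to section 2.1.4 for what the events are and to Table 3 for their criteria. Table 3 is therefore the operative rule.

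**Step 2. Follow each kind of case through the reporting rule into Table 3.**

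| Case | Term the site enters (protocol 10.5.3) | Meets SAP 2.1.4? | Counted by the Table 3 row? |
|---|---|---|---|
| Confirmed rise, no diagnosis | Increased calcitonin | Yes | Yes |
| Confirmed rise, diagnosis other than C-cell disease | The diagnosis | Yes | Only if the query holds that diagnosis |
| Thyroid C-cell neoplasm | The neoplasm | Yes | Only if the query holds C-cell terms |

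Protocol Appendix 3 points the same way: where possible, the diagnosis is recorded in preference to individual signs and symptoms.

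**Step 3. Could the query's content close the gap?** For the third case, yes: the query may hold C-cell neoplasm terms despite its name. For the second case, only awkwardly. A query wide enough to take in autoimmune thyroid disease or chronic renal insufficiency would also count participants with those conditions and no calcitonin rise. Terms alone cannot separate the two groups; the laboratory value can.

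**Step 4. Compare other rows of Table 3.** The pancreatic row adds a separate adverse event category for pancreatic neoplasm to its eCRF page. The cardiovascular row lists four sources. The severe allergic reaction row names several queries. The calcitonin row gives its second component no visible route.

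**Step 5. Where would a missed case still be seen?**
- SAP section 2.4.5.5 summarises calcitonin by treatment group as at or below ULN, above ULN to below 20, 20 to below 50, and 50 ng/L or more. It covers the whole on-treatment period, includes unscheduled values, and adds a listing of participants with out-of-range values. The SAP notes that ng/L equals pg/mL.
- SAP section 2.4.5.1 shows every treatment-emergent diagnosis by preferred term, with separate tables and listings for serious events and for events leading to treatment discontinuation.

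**Step 6. Size of one case.** SAP section 1.3 plans about 100 participants per arm, so about 3 × 100 = 300 on efpeglenatide. One missed case changes an arm's row from 0/100 = 0% to 1/100 = 1%. The number of missed cases cannot be derived: the documents give neither the query's terms nor the share of confirmed rises that reach a diagnosis.

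**Step 7. Threshold.** The unit conversions agree: 5.9/20 = 14.75/50 = 0.295 pmol/L per pg/mL. The inequality does not: protocol section 8.3 uses strictly greater than 20 pg/mL, while SAP section 2.1.4 and protocol section 10.5.3 use greater than or equal. The texts differ only for a value exactly at the threshold, but they need to be reconciled.

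**The case against.** The strongest reply is that a query's name does not reveal its contents. The row is labelled for both components and points to one query, which fits a query built for both. Other single-query rows of Table 3 (acute renal failure, injection site reaction, immune complex disease) also leave their terms to the CMQ, and the pancreatic row needed a separate neoplasm category because it is built from an eCRF page. An AERSM is an adverse event category, so a term query is a natural tool for it, with laboratory values analysed separately in section 2.4.5.5.

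Much of this stands. The comparison with the pancreatic row is suggestive and no more. It cannot be said that C-cell neoplasms are excluded, only that the documents do not show them to be included.

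A reader might go further and infer that a C-cell tumour could go unreported in this study. The documents do not support that. A treatment-emergent tumour would appear by preferred term in the general TEAE tables. Appendix 3 of the protocol says invasive or malignant cancers should usually be considered serious, so it would normally also enter the serious-event table and listing. A calcitonin rise in the on-treatment period would appear in the laboratory categories whatever term the site used.

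The reply does not cover the second case in the table. A confirmed rise reported under a diagnosis other than C-cell disease meets the SAP's definition and can fall outside the row even if the query holds every C-cell term. The laboratory table shows the value but does not correct the AERSM count, overview or listing, which exist to bring these cases together.

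**Conclusion.** The point holds in a limited form. Table 3 states a rule that can undercount the event the SAP itself defines. The effect is confined to the AERSM row, the AERSM overview count and the AERSM listing. For confirmed rises reported under another diagnosis, it rests on the reporting rule in protocol section 10.5.3 and on a query that works from terms. For C-cell neoplasms, it depends also on the query omitting them, which cannot be checked from the documents.

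Two other readings go too far. One is that every confirmed rise with a diagnosis is lost from the row; without the term list that is unknown, and a site could enter a calcitonin term as well. The other is to attach a percentage to the undercount; that needs the share of confirmed rises with a diagnosis, and no section gives it. What can be said is that one case moves an arm of about 100 from 0% to 1%. The primary and secondary efficacy analyses are unaffected. This is a cheap improvement, not a threat to the trial's conclusions.

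**What to change.** Replace the Table 3 criterion for this row with any of:

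- (a) central-laboratory calcitonin at or above 20 pg/mL, confirmed on the retest in protocol section 10.5.3, whatever adverse event term was reported;
- (b) the existing calcitonin increase CMQ;
- (c) a term for thyroid C-cell neoplasm or hyperplasia, or medullary thyroid cancer.

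Show the calcitonin and neoplasm components as separate sub-rows. Append the CMQ term list to the SAP; if it already holds the C-cell terms, part (c) only needs to say so. Reconcile the strict inequality in protocol section 8.3 with the inclusive one in SAP section 2.1.4 and protocol section 10.5.3, so that (a) rests on one stated threshold.

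The cost is one table cell and a small derivation from laboratory data already collected. Section 2.4.5.5 already covers most of it; what is new is the confirmation on retest and the link to the AERSM row. The count may come out slightly higher. No new data and no change to the management of participants are needed.
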